Subjects are advised to avoid using contact lenses while on MIRV except when benefit outweighs risk per an eye care professional. Eyelid hygiene should be performed as per direction of an eye care professional. Please refer to Section [5.3.2.2](#) for details on the use of lubricating artificial tears and recommendations for prophylactic steroid eye drops in subjects with ocular symptoms. The use of UVA/UVB sunglasses in full daylight is recommended during the study. If subjects report signs or symptoms of ocular AEs, including but not limited to blurred vision or eye irritation, the management and dose modification guidelines outlined in [Table 8](#) and [Table 9](#) should be followed.

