3.7.3.5.2 Management and Dose Modifications Guidelines [MIRV Cohort]

If a subject develops new CTCAE $>$ Grade 1 ocular symptoms, MIRV will be held until the subject undergoes a complete examination by an eye care professional. If a subject is found to have confluent superficial keratitis, a cornea epithelial defect, or a 3-line or more loss in BCVA, MIRV dosing must be interrupted until findings improve to nonconfluent keratitis, prior baseline, or complete resolution. Uveitis must improve to Grade 1 or better or prior baseline. Treatment with MIRV may resume if the ocular event improves as above within 28 days of the next scheduled MIRV dose (refer to [Table 8](#) and [Table 9](#) for details). Corneal AEs of any severity should be followed to complete resolution, pretreatment baseline, or are deemed to be irreversible according to the eye care professional. For 2 or more overlapping ocular adverse events (ocular disorders/corneal adverse reactions), dose modification should be based on the ocular adverse event of greater severity. Any other ocular AEs not specifically noted in [Table 8](#) or [Table 9](#) will be managed at the discretion of the treating physician in consultation with their eye care professional.

Subsequent eye examinations will be scheduled to occur in every other cycle going forward from the time that the corneal AE was initially reported until resolution of the corneal toxicity to subject's prior baseline or complete resolution or until it is deemed irreversible even if the results of the subject's ocular symptom assessment show no obvious clinical findings. For subjects with ongoing keratitis/keratopathy, a cornea epithelial defect, or a 3-line or more loss in BCVA at the PTV, an ophthalmic examination should be done every 30 days until complete resolution, stabilization without likelihood of improvement in the opinion of the eye care professional, or return to pretreatment baseline. Ocular symptoms (e.g., blurred vision) should also be assessed at this time. The visual acuity assessment should be performed with refraction, rather than corrected or via pin hole. Refraction is crucial for cases where subjects report blurred vision or other ocular AEs.

Management of ocular AEs with inflammatory characteristics or other non-corneal/visual acuity ocular AEs should include measures as indicated by an eye care professional.

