Recommended dosage modifications for corneal AEs should be based on both corneal examination findings using the system outlined in [Table 8](#) and changes in BCVA. Dose modifications for non-corneal ocular AEs are at the discretion of the treating physician, in collaboration with an eye care professional.

Note: [Table 8](#) describes the management of corneal adverse reactions with regard to MIRV dosing. See [Table 15](#) and [Table 16](#) in Appendix Section [16.6](#) for grading of ocular AEs.

Table 8 Management of Corneal Adverse Reactions (Keratitis/Keratopathy)

Ocular Exam Finding ^a	Management	Guidelines for MIRV Dose Modification
Nonconfluent superficial keratitis or nonconfluent keratopathy ^b	Complete eye examination as outlined in SOA (Section 6.2). Subjects should have frequent symptomatic ocular assessments and repeat eye examinations at least every 6 weeks until resolved to pretreatment baseline or nonconfluent superficial keratitis or better or are deemed to be irreversible by the investigator, even after treatment discontinuation, if needed	Monitor with scheduled ocular exam to complete resolution or return to pretreatment baseline. Continue MIRV dosing.
Confluent superficial keratitis or confluent keratopathy ^b , cornea epithelial defect (+NaFl staining), or \geq 3-line loss in BCVA	Complete eye examination as outlined in SOA (Section 6.2). Subjects should have weekly symptomatic ocular assessments and repeat eye examinations at least every 6 weeks until resolved to pretreatment baseline or are deemed to be irreversible by the investigator, even after treatment discontinuation, if needed.	Hold MIRV dosing until AE has resolved to pretreatment baseline or nonconfluent superficial keratitis or better. Subjects with corneal adverse reactions lasting $<$ 14 days may be allowed to resume MIRV at the same dose level. Recurrence of toxicity on subsequent cycles despite best supportive care will require a dose reduction to one lower dose level. Subjects with corneal adverse reactions lasting \geq 14 days but no more than 28 days may resume MIRV at one lower dose level. If findings persist $>$ 28 days, continuation at reduced dose level is at the discretion of the investigator in consultation with the Sponsor.

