Corneal ulcer or clinically significant stromal opacity or BCVA 20/200 or worse	Complete eye examination as outlined in SOA (Section 6.2). Subjects should have weekly symptomatic ocular assessments and repeat eye examinations at least	Hold MIRV dosing. Subjects may be allowed to resume MIRV at one lower dose level after AE has resolved to

Ocular Exam Finding ^a	Management	Guidelines for MIRV Dose Modification
	every 6 weeks until resolved to baseline or are deemed to be irreversible by the investigator, even after treatment discontinuation, if needed.	nonconfluent keratitis or better or to pretreatment baseline within 28 days. If findings persist >28 days, continuation at reduced dose level is at the discretion of the investigator in consultation with the Sponsor.
Corneal perforation	Complete eye examination as outlined in SOA (Section 6.2). Subjects should have weekly symptomatic ocular assessments and repeat eye examinations at least every 6 weeks until resolved to baseline or are deemed to be irreversible by the investigator, even after treatment discontinuation, if needed.	Permanently discontinue MIRV dosing.

^a Normal = clear cornea, no epithelial defects.

^b Nonconfluent microcystic epithelial change, punctate epithelial keratopathy, subepithelial inclusion cyst and/or nonconfluent superficial keratitis, superficial punctate keratitis, epithelial erosion

Table 9 Management of Ocular Disorders

Refer to [Table 8](#) for Corneal Adverse Reactions.

Severity Grade (CTCAE v5.0)	Management	Guidelines for MIRV Dose Modifications
Grade 1	Follow SOA (Section 6.2) Monitor for worsening symptoms	Continue MIRV dosing
Grade 2	Complete eye exam as outlined in SOA (Section 6.2) Repeat complete exam as clinically indicated. Subjects should have weekly symptomatic ocular assessments by the investigator until the symptoms resolve to Grade \leq 1 or are deemed to be irreversible by the investigator.	Hold MIRV dosing until AE has resolved to Grade 1 or better. Subjects with ocular symptoms lasting < 14 days may be allowed to resume MIRV at the same dose level. Subjects with ocular symptoms lasting \geq 14 days but no more than 28 days may resume MIRV at one lower dose level. Recurrence of Grade 2 toxicity on subsequent cycles despite best supportive care will require a MIRV dose reduction of one dose level.

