Grade 3	Complete eye exam as outlined in SOA (Section 6.2). Repeat complete exam as clinically indicated. Subjects should have weekly symptomatic ocular assessments by the investigator until the symptoms resolve	Hold MIRV dosing. Subjects may be allowed to resume MIRV at a lower dose after AE has resolved to Grade 1 or better within 28 days. Recurrence of Grade 3 toxicity on subsequent cycles despite best supportive care will require a MIRV dose reduction of one dose level.

Severity Grade (CTCAE v5.0)	Management	Guidelines for MIRV Dose Modifications
	to Grade \leq 1 or are deemed to be irreversible by the investigator.	
Grade 4	Complete eye exam as outlined in SOA (Section 6.2). Repeat complete exam as clinically indicated. Subjects should have weekly symptomatic ocular assessments by the investigator until the symptoms resolve to Grade \leq 1 or are deemed irreversible by the investigator.	Permanently discontinue MIRV.

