16.6 Grading of Ocular AEs [MIRV Cohort Only]

Table 15 Grading for Ocular Symptoms

Ocular AE	Grade 1	Grade 2	Grade 3	Grade 4
Blurred Vision A disorder characterized by visual perception of unclear or fuzzy images	Intervention not indicated	Symptomatic; limiting instrumental ADL ¹	Symptomatic; Limiting self-care ADL ²	Blindness in the affected eye
Dry Eyes A disorder characterized by dryness of the cornea and conjunctiva.	Asymptomatic; clinical or diagnostic observations only; symptoms relieved by lubricants	Symptomatic	Symptomatic; limiting self-care ADL ²	--
Eye Pain A disorder characterized by a sensation of marked discomfort in the eye.	Mild pain	Moderate pain; limiting instrumental ADL ¹	Severe pain; limiting self-care ADL ²	--
Floater A disorder characterized by an individual seeing spots before their eyes. The spots are shadows of opaque cell fragments in the vitreous humor or lens.	Symptomatic but not limiting ADL	Limiting instrumental ADL ¹	Limiting self-care ADL ²	--
Photophobia A disorder characterized by fear and avoidance of light.	Symptomatic but not limiting ADL	Limiting instrumental ADL ¹	Limiting self-care ADL ²	--

Abbreviations: ADL = activities of daily living

Table 16 Grading for Other Ocular Events

Ocular AE	Grade 1	Grade 2	Grade 3	Grade 4
Cataract A disorder characterized by partial or complete opacity of the crystalline lens of one or both eyes. This results in a decrease in visual acuity and eventual blindness if untreated.	Asymptomatic; clinical or diagnostic observation only; intervention not indicated	Symptomatic; glare symptoms affecting instrumental ADL ¹	Symptomatic limiting self-care ADL ²	Blindness in the affected eye
Conjunctivitis A disorder characterized by inflammation, swelling and redness to the conjunctiva of the eye.	Asymptomatic or mild symptoms; intervention not indicated	Symptomatic	Symptomatic; limiting self-care ADL ²	Blindness in the affected eye

Ocular AE	Grade 1	Grade 2	Grade 3	Grade 4
Decline in Best Corrected Visual Acuity (BCVA) (Vision Decreased) A disorder characterized by a decrease in visual acuity from baseline	--	Moderate decrease in visual acuity (BCVA 20/40 and better or 3 lines or less decreased vision from known baseline)	Marked decrease in visual acuity (BCVA worse than 20/40 or more than 3 lines of decreased vision from known baseline, up to 20/200)	BCVA worse than 20/200 in the affected eye

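### The protocol's ocular dose-modification provisions for MIRV contradict each other on who decides for non-corneal events and on the outcome for visual acuity worse than 20/200

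*Protocol*

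**What the plan says.** **Non-corneal events.** Protocol Section 3.7.3.5.2 says, just before Table 8: "Dose modifications for non-corneal ocular AEs are at the discretion of the treating physician, in collaboration with an eye care professional". Section 3.7.3.5.1 says that when a subject reports ocular signs or symptoms, "the management and dose modification guidelines outlined in" Tables 8 and 9 should be followed. An earlier paragraph of 3.7.3.5.2 says that ocular AEs not specifically noted in either table "will be managed at the discretion of the treating physician in consultation with their eye care professional". That paragraph also sets a recovery level for uveitis, which is not a corneal event.

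Table 9 refers corneal adverse reactions to Table 8 and gives an action by grade for the rest:
- Grade 1: continue.
- Grade 2: hold, then resume according to how long the event lasted.
- Grade 3: hold, with resumption at a lower dose possible if the event resolves within 28 days.
- Grade 4: "Permanently discontinue MIRV".

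**Severe loss of acuity.** One row of Table 8 is "Corneal ulcer or clinically significant stromal opacity or BCVA 20/200 or worse". Its action is to hold, after which "Subjects may be allowed to resume MIRV at one lower dose level after AE has resolved to" a stated level within 28 days. If findings persist longer, continuation at a reduced level remains possible after consultation with the sponsor. In Appendix 16.6, Table 16 defines Grade 4 decline in BCVA as "BCVA worse than 20/200 in the affected eye". Grade 3 runs up to 20/200.

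**Grading source.** Sections 3.5, 3.7 and 9.2.4, and the note above Table 8, send ocular grading to Appendix 16.6. Table 9 is headed with CTCAE v5.0. CTCAE grades are also the ocular trigger in Sections 3.7.3.5.1, 3.7.3.5.2 and 6.5.7 and in footnotes g and j of the Section 6.2 schedule.

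**The concern.** An investigator with a subject in front of them needs one answer. For a Grade 2 or Grade 3 non-corneal event, one sentence leaves the MIRV dose to the physician and a table a page later prescribes a hold. For acuity worse than 20/200, one table permits resumption and another ends MIRV. If the grading scale is also unclear, two sites could disagree even on which row of Table 9 applies.

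Patient safety comes first. There is also a data consequence. AEs leading to discontinuation are a primary outcome measure (Protocol Section 2), and SAP Section 8.3 tabulates AEs leading to drug withdrawal separately for MIRV. If the protocol supports two actions for one event, that table partly reflects which provision a site happened to follow.

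**Working it through.** The plan states no figure on this point, so the check is a comparison of provisions.

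**1. Who decides for non-corneal events**

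| Provision | Instruction |
|---|---|
| 3.7.3.5.2, sentence before Table 8 | Physician discretion for all non-corneal ocular AEs |
| 3.7.3.5.2, earlier paragraph | Discretion only for ocular AEs in neither table; recovery level set for uveitis |
| 3.7.3.5.1 | Follow Tables 8 and 9 |
| Table 9 | An action for each of Grades 1 to 4 |

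Table 9 hands corneal reactions to Table 8, so what it keeps is the non-corneal disorders. These are the same events that the first row leaves to discretion. The first row therefore conflicts with the other three, and no sentence says which prevails.

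**2. Acuity, by level**

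| BCVA | Table 16 grade | Table 8 | Table 9 at that grade |
|---|---|---|---|
| Exactly 20/200 | 3 | Hold; may resume lower | Hold; may resume lower |
| Worse than 20/200 | 4 | Hold; may resume lower | Permanent discontinuation |

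At exactly 20/200 the actions are compatible. The conflict starts at anything worse. Two provisions might resolve it:
- *Table 9's cross-reference to Table 8.* This can route corneal vision loss to Table 8 alone. But the acuity trigger in Table 8 is joined by "or" to the corneal findings and names no cause, and Table 16 grades acuity decline whatever its cause. For non-corneal loss the routing is not stated.
- *The greater-severity rule in 3.7.3.5.2.* This is written for two or more overlapping events, and it needs a severity for each. Table 8 rows carry no grades, so there is nothing to compare with a Table 9 grade.

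**3. How many subjects**

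The inputs are the Phase 3 rates in Section 3.7.3.5 and the approximately 70 MIRV subjects in Section 3.3.2. Expected subjects = 70 × rate.

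| Event | All grades | Grade 3 or higher |
|---|---|---|
| Blurred vision | 70 × 0.42 = 29.4 | 70 × 0.02 = 1.4 |
| Eye pain | 70 × 0.13 = 9.1 | 70 × 0.01 = 0.7 |
| Photophobia | 70 × 0.12 = 8.4 | 70 × 0.01 = 0.7 |

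The all-grade column is only a ceiling. Table 9 continues dosing at Grade 1, no separate Grade 2 rate is given, and the events are not split into corneal and non-corneal. The documents therefore do not give the number affected.

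**The case against.** Four points can be made for the plan.

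- *Section 3.7 says the toxicity guidelines are not prescriptive.* True, and it softens the force of Table 9. It does not say which of two opposite instructions an investigator should start from, and Table 9 is worded as directions.
- *The discretion sentence is one loosely worded line, and the neighbouring text points to the tables.* This is a fair account of how the conflict may have arisen. The sentence is still in the current text, without limits.
- *Corneal vision loss goes to Table 8 only.* This reading is reasonable, and it narrows the second conflict. A reader might infer that every subject with acuity worse than 20/200 has two prescribed outcomes. The documents do not support that for clearly corneal loss. They do leave the routing open otherwise.
- *The practical effect may be small.* A reader might infer that some 29, 9 and 8 of 70 subjects are affected. Those are all-grade counts of events that Section 3.7.3.5 introduces as consistent with keratopathy, so they cannot be assigned to the non-corneal conflict. A reader might also infer that each disputed case moves the expansion stopping boundary (8 at 20 subjects in Section 9.1.3.2) by one. That is not supported either. Holds and reductions do not count, and resumption under Table 8 is permitted but not required. Section 9.1.3 speaks of discontinuing SL-172154 and a combination agent, while 9.1.3.2 speaks of treatment discontinuation and Section 3.11 lets one agent continue alone. Whether stopping MIRV only would count is unsettled.

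**Conclusion.** The contradictions are real. The first is direct: unlimited discretion for non-corneal ocular AEs against grade-by-grade actions for the same events. The second is narrower: it applies to acuity worse than 20/200, and is clearest where the loss is not plainly corneal. The split between CTCAE and Appendix 16.6 adds uncertainty about which grade triggers a Table 9 action.

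The size cannot be derived from the documents. Severe events are few, at about 1 of 70 subjects per event if the cited Phase 3 rates carry over to this cohort. Grade 2 events may add more, by an unknown amount. Any effect on the stopping boundary is uncertain. The point rests on an unclear safety rule and on inconsistent classification of AEs leading to MIRV withdrawal, and not on a count. It should be corrected, and it does not threaten the design.

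**What to change.** Reconcile Protocol Sections 3.7, 3.7.3.5.1 and 3.7.3.5.2 (including Tables 8 and 9) and Table 16 in Appendix 16.6, so that:

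1. one provision is stated to govern dose modification for non-corneal ocular AEs, with the scope of any physician discretion worded the same way throughout;
2. BCVA worse than 20/200 has one stated routing between Tables 8 and 9, for corneal and non-corneal causes, and one outcome;
3. the greater-severity rule can be applied to a Table 8 finding, or its limits are stated;
4. the grading source that triggers Table 9 actions is named consistently there, in Sections 3.7.3.5.1, 3.7.3.5.2 and 6.5.7, and in footnotes g and j of Section 6.2.

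Which clinical rule applies, and which scale, is for the sponsor to decide. The cost is wording in a few sections and tables, a protocol amendment or clarification memo, and notice to MIRV sites. No analysis in the SAP changes.

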3.7.3.5.1 Monitoring and Preventive Measures [MIRV Cohort]

In early dose escalation there was a relationship observed between MIRV plasma exposure and likelihood of an ocular event as well as with response. Exposure-response modeling suggested that a dose of 6.0 mg/kg AIBW provided adequate exposure for response while also maintaining overall exposure within a range that decreased the potential for ocular AEs. Due to the observation of ocular disorders consistent with reversible keratopathy/corneal epitheliopathy in subjects treated with MIRV, ocular function will be carefully monitored. Ocular symptom assessments will be performed at baseline and at Day 1 of every cycle thereafter (Section 6.2).

A complete ophthalmic examination will be performed in all subjects receiving MIRV by an ophthalmologist, optometrist, physician assistant, or equivalent eye care professional and will include the following at a minimum: manifest refraction, best distance corrected visual acuity (BCVA), intra-ocular pressure (IOP) assessment, fundoscopy, and slit lamp examination to assess the cornea for keratopathy and other corneal abnormalities. The visual acuity assessment should be performed with refraction, rather than corrected or via pin hole. Fundoscopy is required at baseline and post-treatment visit (PTV) only.

- A complete ophthalmic examination will be performed in all subjects receiving MIRV at baseline (within 21 days before C1D1), prior to Day 1 dosing in Cycles 3, 5, and 7 and at

the PTV (\pm 2 weeks) including subjects who are asymptomatic or have \leq Grade 1 ocular AEs. Abnormal corneal findings in asymptomatic subjects will be managed as per [Table 8](#).

- Subjects receiving MIRV who experience CTCAE $>$ Grade 1 ocular AEs while on study will have a complete ophthalmologic examination performed at the emergence of symptoms and at every other cycle thereafter until resolved to baseline or deemed irreversible in the opinion of the eye care professional. Subjects requiring an ophthalmological examination due to symptoms prior to Cycle 2 or 4 will then proceed to every other cycle (approximately 6 weeks) exams as indicated by findings and do not require the routine, asymptomatic exams at Cycle 3, 5, and 7.

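### Table 8, row 1: the Management cell's end point for repeat eye examinations is already met when nonconfluent superficial keratitis is found, and it conflicts with its own row and with Section 3.7.3.5.2

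*Protocol*

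**What the plan says.** Table 8 in Protocol Section 3.7.3.5.2 has four rows of corneal findings. Row 1 is for nonconfluent superficial keratitis or nonconfluent keratopathy. It is the only row in which MIRV continues without a hold: rows 2 and 3 hold dosing and row 4 stops it permanently.

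- **Row 1, Management cell:** "repeat eye examinations at least every 6 weeks until resolved to pretreatment baseline or nonconfluent superficial keratitis or better", or until the investigator judges the finding irreversible.
- **Row 1, dosing cell:** "Monitor with scheduled ocular exam to complete resolution or return to pretreatment baseline", with MIRV continued.
- **Section 3.7.3.5.2, text before the table:** "Corneal AEs of any severity should be followed to complete resolution, pretreatment baseline, or are deemed to be irreversible", the last being for the eye care professional to judge. On timing: "Subsequent eye examinations will be scheduled to occur in every other cycle going forward from the time that the corneal AE was initially reported", ending at "prior baseline or complete resolution or until it is deemed irreversible". This applies even when the symptom assessment shows nothing.
- **Section 3.7.3.5.1:** "Abnormal corneal findings in asymptomatic subjects will be managed as per" Table 8. Routine examinations take place at baseline, "prior to Day 1 dosing in Cycles 3, 5, and 7", and at the post-treatment visit (PTV).
- **Section 6.5.8:** event-driven examinations end at baseline or wherever Tables 8 and 9 say.

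**The concern.** A stopping rule should describe a state that the subject is not yet in. For nonconfluent superficial keratitis, the Management cell lists the entry finding itself among the states that end follow-up. Read literally, the cell asks for no repeat examination.

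What is at stake is corneal monitoring during treatment. Under row 1 the subject goes on receiving MIRV. Progression to confluent keratitis or an epithelial defect would trigger a hold, and in a subject without symptoms it is found by examination. If sites apply different end points, that monitoring depends on which cell or section a site happens to follow.

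**Working it through.** No sample size, power or event count is involved, so the check sets the stopping rules side by side. The last column takes the finding as new since baseline.

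| Place in the protocol | Repeat examinations end at | Already met by nonconfluent superficial keratitis at detection? |
|---|---|---|
| Table 8 row 1, Management cell | baseline; nonconfluent superficial keratitis or better; irreversible (investigator) | Yes |
| Table 8 row 1, dosing cell | full resolution; baseline | No |
| Section 3.7.3.5.2 text, any severity | baseline; full resolution; irreversible (eye care professional) | No |
| Section 3.7.3.5.1, ocular events above Grade 1 | baseline; irreversible (eye care professional) | No |
| Section 6.5.8 | baseline; or as Tables 8 and 9 say | Depends on which row 1 cell is read |
| Table 8 rows 2 to 4, Management cells | baseline; irreversible (investigator) | Not applicable; the extra phrase is absent |

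**Frequency.** Every other 21-day cycle is 2 × 21 = 42 days, or 6 weeks, the same as the minimum frequency in row 1. The rules agree on how often to examine and differ on when to stop.

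**Keratitis and keratopathy.** The phrase names keratitis only. Table 8 footnote b lists keratitis and keratopathy findings together without ranking them. For a subject who enters row 1 with nonconfluent keratopathy, it is therefore less certain that the end point is met at detection.

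**Where the phrase fits.** The row 2 dosing cell reads "Hold MIRV dosing until AE has resolved to pretreatment baseline or nonconfluent superficial keratitis or better". There the subject starts from confluent disease, so the phrase marks a real improvement. That it was carried into row 1 by mistake is an inference that the documents do not settle.

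**When the conflict matters most.** Without delays, Day 1 of Cycle k falls on study day 1 + (k − 1) × 21:

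- Cycle 3: 1 + 2 × 21 = Day 43
- Cycle 5: 1 + 4 × 21 = Day 85
- Cycle 7: 1 + 6 × 21 = Day 127

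A finding first seen at the Cycle 3 or Cycle 5 examination meets another routine examination 42 days later, whichever rule is applied. A finding first seen at Cycle 7 meets none until the PTV. Treatment beyond Cycle 7 is foreseen, since the scan schedule in Section 6.11 runs through Cycle 27 and on. For each further 42 days on MIRV with the finding still present, the Section 3.7.3.5.2 text calls for one examination and the Management cell read alone calls for none.

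**The case against.** The strongest answer is that the protocol already requires the follow-up. The Section 3.7.3.5.2 text covers corneal events of any severity, sets the interval and says that a clean symptom assessment does not end it. The adjacent cell of row 1 also asks for monitoring to an end point not met at detection. A note above Table 8 describes the table as concerned with MIRV dosing. Ocular symptoms are assessed before each cycle, and keratitis or keratopathy still present at the PTV is examined every 30 days.

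Much of this stands. A reader might infer from the one cell that event-driven examinations can simply stop at onset. The documents do not support that: they stop early only where a site follows the Management cell over its neighbour and the section text.

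The objection does not remove the conflict. Section 3.7.3.5.1 sends asymptomatic corneal findings to Table 8, and Section 6.5.8 lets Table 8 set the end of examinations. A site that uses the Management cell is therefore following the protocol. The routine examinations are an incomplete backstop, because none falls between Cycle 7 and the PTV. Subjects examined for symptoms before Cycle 2 or 4 are excused the routine ones and move to every-other-cycle examinations as findings indicate. Examinations after the PTV do not help during treatment.

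Two further inferences also fail:

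- **Time to resolution.** A reader might think that time to resolution of keratopathy is cut off at onset. It is not an outcome in Protocol Section 2, and the SAP's table list has no such output. Sections 6.5.7, 7 and 7.4 set adverse event follow-up separately from Table 8.
- **Number harmed.** Section 3.7.3.5 gives keratopathy in 33% of subjects in the Phase 3 MIRV study. Applied to 12 + 64 = 76 planned MIRV subjects, that is 0.33 × 76 ≈ 25. This approximates subjects with any keratopathy, not subjects who lose an examination. The documents give neither the nonconfluent share nor the share first seen at Cycle 7 without symptoms.

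**Conclusion.** The point holds as an internal contradiction in an operative safety rule. For nonconfluent superficial keratitis, the Management cell's end point is met at detection, and it conflicts with the dosing cell of the same row and with the Section 3.7.3.5.2 text. For nonconfluent keratopathy the same reading is possible but less certain.

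The effect is that sites may differ in corneal monitoring while MIRV continues. It is largest for an asymptomatic finding first seen at the Cycle 7 examination. That assumes cycles without delay, treatment continuing past Cycle 7, and a site that follows the Management cell. The number of such subjects cannot be estimated from the documents. No endpoint, sample size or planned analysis is affected.

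**What to change.** Reconcile the two cells of Table 8 row 1, the Section 3.7.3.5.2 text and the cross-reference in Section 6.5.8. One follow-up end point should apply to row 1 findings, and it should not be already met when the finding is detected. State whether it covers keratitis and keratopathy alike. In the same edit, settle who judges irreversibility: Table 8 names the investigator, while Sections 3.7.3.5.1 and 3.7.3.5.2 name the eye care professional. The sponsor's ocular advisers choose the end point; this review does not propose one.

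The cost is about one phrase in Table 8 plus the matching wording elsewhere. Keeping the follow-up that the Section 3.7.3.5.2 text already requires would add no procedure.
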